### **3.2 Exclusion criteria**

1. Any previously confirmed form of cancer other than surgically treated non-invasive uterine cancer or basal cell carcinoma treated with surgery or radiotherapy.
2. Proven visceral and/or bone metastases or diffuse metastases.
3. Life-threatening infection and/or heart failure and/or liver failure and/or other life-threatening systemic conditions.
4. Ascites.
5. Significantly reduced lung function.
6. Age under 18.
7. Coagulation system disorders.
8. Received cumulative dose of bleomycin  $\geq 250 \text{ mg/m}^2$ .
9. Allergic reactions to previous treatment with bleomycin.
10. Chronic decrease in renal function (creatinine  $> 150 \text{ }\mu\text{mol/L}$ ).
11. Epilepsy
12. Heart rhythm disorders.
13. Implanted pacemaker or defibrillator.
14. Pregnancy.
15. Patients who are unable to understand the purpose of the study.

### **3.3 Examinations and tests before treatment**

Two weeks before inclusion in the study, the following will be performed:

- clinical examination, anamnesis
- radiological imaging techniques to discover liver metastases:
  - dynamic contrast-enhanced magnetic resonance imaging (DCE-MRI)
  - dynamic contrast-enhanced ultrasound (DCE-US)
  - computed tomography (CT) perfusion
- Testing for systemic metastases
  - CT of the lungs
  - other examinations depending on the clinical picture (bone scintigraphy, PET/CT)

One week before inclusion in the study, the following will be performed:

- laboratory tests:
  - haematological tests with a complete blood count
  - coagulation tests
  - biochemical tests: electrolytes, creatinine, transaminases
  - immunohistochemical examinations: tumour markers
- ECG

In patients for whom two-stage surgery is planned, the following will be performed:

- histological analysis of liver metastases and comparison of pathohistological changes between treated and untreated metastases.

[figure not shown]
#### **4 TREATMENT PLAN**

When there are liver metastases (up to 3 cm in maximum diameter) with the lower edge located up to 3 cm below the liver capsule, ECT using short needle electrodes with a hexagonal geometric arrangement will be performed in line with standard surgical procedures for treating cutaneous and subcutaneous tumours/metastases with ECT.

When there are larger liver metastases (up to 5 cm) located near the vena cava or along large hepatic or portal veins, ECT using long needle electrodes with an arbitrary geometric arrangement will be performed. Using numerical modelling, we will prepare a treatment plan to determine the optimal position of the electrodes and the required electric current voltage for optimal electroporation of the target tissue. The preparation of a treatment plan using numerical modelling will take place in two basic steps (see below) based on radiological images captured up to 2 weeks before the procedure.

1. Decomposing medical images and constructing a model:
  - importing medical radiology images into an appropriate program,
  - determining important areas,
  - pre-treating and decomposing images,
  - constructing a 3D model.
2. Planning treatment:
  - The 3D model will be supplemented with electrodes supplying electroporation pulses, and with corresponding tissue properties and boundary conditions based on the calculation using the finite element method and the calculation processed by automatic algorithms for determining the criterion function,

- the possibility of statistical and probability functions to determine the probability of electroporation will be examined, the effect probability being a function of the electric field strength applied.

*Figure 1: Schematic representation of electrode placement in the middle and the periphery of a metastasis in healthy liver tissue.*

## 5 TREATMENT: ELECTROCHEMOTHERAPY (ECT)

Patients with multiple bilateral metastases scheduled for two-stage surgery depending on their general condition and extent of the disease will have their right portal vein ligated and up to 3 metastases treated on the right hepatic lobe with up to 3 cm in maximum diameter using ECT during the first surgical procedure. On the left, metastases will be treated using established methods, such as surgery and RFA. During the second procedure, the entire right half of the liver will be removed.

In patients with liver metastases in areas where, due to the proximity of the main hepatic veins, surgery is not possible and the success of other ablation techniques cannot be predicted, ECT will be performed.

### 5.1 Chemotherapeutic agents

- The cytostatic used will be bleomycin (BLM) manufactured by Heinrich Mack Nachf. GmbH & Co. KG, Illertissen, Germany.
- BLM will be dissolved in saline solution and administered intravenously with a bolus injection at a dose of 15 mg/m^2.
- 8–28 min after BLM application, electroporation pulses will be delivered to the metastases.

## 5.2 Electroporation

### 5.2.1 Electric pulse generator

- We will use the Cliniporator VITAE electric pulse generator manufactured by IGEA, Carpi, Italy, designed to treat larger and deep-seated tumours, such as liver metastases.
- It has the CE mark and is authorized for use in a clinical setting.

### 5.2.2 Electrodes

Two types of electrodes will be used:

- a) short needle electrodes with a fixed hexagonal geometric arrangement:
  - for metastases with their lower edge located up to 3 cm below the liver capsule;
  - ECT will be performed in line with standard surgical procedures for cutaneous and subcutaneous tumours/metastases;
- b) long needle electrodes with an arbitrary geometric arrangement:
  - for deeper-seated tumours and tumours located  $\geq 3$  cm below the liver capsule;
  - to capture the safety margin, the required number of electrodes (presumably from 4 to 6) will be inserted into the metastasis and its surroundings using ultrasound guidance in line with the treatment plan prepared based on numerical modelling before the procedure.

[figure not shown]

Figure 2 Short needle electrodes with a fixed hexagonal geometric arrangement (a), long needle electrodes with an arbitrary geometric arrangement (b) and Cliniporator VITAE (c).

### **5.2.3 Electroporation pulses**

- Between each pair of electrodes, 8 rectangular electroporation pulses (length: 100  $\mu$ s) will be supplied to the metastases in two trains, each containing 4 electroporation pulses of reversed polarity and a repeating frequency of 1000 Hz.
- The delivery of individual pulse trains will be synchronized with the occurrence of successive heartbeats.
- When using long needle electrodes with an arbitrary geometric arrangement, the voltage of electroporation pulses for each electrode pair will be determined on the basis of numerical modelling, and when using short needle electrodes with a fixed hexagonal geometric arrangement, a voltage of 730 V will be applied.
- If excessive electric current ( $> 50$  A) makes it impossible to supply a sufficiently high voltage, a larger number of lower-voltage electroporation pulses will be supplied.

### **5.3 Synchronization of electroporation pulses with ECG and Holter ECG recording**

- To ensure synchronization, the Cliniporator VITAE will be connected to an AccuSync 42 external unit, which produces trigger pulses based on the measured ECG signal to deliver electroporation pulses on the R wave of each heartbeat.
- For interoperative patient monitoring, patients will be connected to AccuSync via three ECG electrodes independently of ECG capture.
- On the selected ECG lead (standard leads I, II, III; the most suitable lead is chosen depending the intensity of the R wave), AccuSync detects the R wave of individual heartbeats in the early phase of increasing R wave slope, and produces a trigger pulse.
- The trigger pulse is brought to the Cliniporator VITAE, which uses its built-in synchronization algorithm for a further verification of trigger pulse suitability, and, meeting a series of conditions, produces electroporation pulses with a 50 ms delay behind the trigger pulse to avoid ventricular sensitivity (T wave range).
- ECG signal and trigger pulses will be captured and stored for later analysis of the synchronization algorithm function and of any immediate effects of treatment on heart function.

## **6 FOLLOW-UP AFTER TREATMENT**

Follow-up will be carried out at three levels. First, defining the early and late effects of treating colorectal liver metastases using ECT; second, evaluating short- and/or long-term effects of electroporation pulses, BLM or ECT as a whole on heart function; and third, recording adverse effects of ECT.

### 6.1. Effects of treating colorectal liver metastases using ECT

- Early treatment effects will be assessed using DCE-US or CT based on changes in tumour blood flow after ECT compared to pre-ECT blood flow.
- Late effects will be assessed based on modified RECIST criteria, taking into account the change in the size and density of treated tumour nodules before and after ECT. These will be assessed based on DCE-MRI images; the volume of the metastases will be calculated using the formula  $V = \frac{a \times b^2 \times \pi}{6}$ , where a is the shorter and b the longer metastasis diameter.

Based on the assessment of the late ECT effects, the response to treatment will be evaluated in line with the WHO classification:

- Complete response (CR): complete disappearance of the tumour nodule
  - Partial response (PR): reduction of tumour nodule size by more than 50%
  - No change (NC): decrease in tumour nodule size by less than 50% or increase in tumour nodule size by less than 25%
  - Progressive disease (PD): growth of the tumour nodule by more than 25%
- The direct effect will be assessed by histological analysis of those metastases that will be surgically removed.
  - EORTC Quality of Life questionnaire according to QLQ C30 standards

EXAMINATION/TEST	Screening period until D -14	D -1	D 7	D 30	D 60	D 90	D 120
clinical examination, anamnesis	X	X	X	X	X	X	X
ECG	X	X					

DCE-MRI	X			X		X
DCE-US	X			X	X	X
CT perfusion	X			X		X
Blood count	X	X	X			
Coagulation tests	X	X	X			
Biochemical blood analysis	X	X	X	X	X	X
EORTC QLQ C30 questionnaire	X		X	X		

\*D = day

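### The tumour volume formula in Section 6.1 squares the longer diameter; volumes are larger than the usual form by longer/shorter, and PR, NC and PD can shift if 'size' means this volume and lesions change shape

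*Combined protocol and SAP*

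**What the plan says.** Section 6.1 has late treatment effects read from DCE-MRI: "Late effects will be assessed based on modified RECIST criteria, taking into account the change in the size and density of treated tumour nodules". The same bullet gives a volume for each lesion, V = a × b² × π/6. Its definition of the two letters reads "where a is the shorter and b the longer metastasis diameter", which makes the squared term the longer one.

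The section then turns to the WHO classification and grades each treated nodule:

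- The rule for CR is: "Complete response (CR): complete disappearance of the tumour nodule".
- The rule for PR is: "reduction of tumour nodule size by more than 50" per cent.
- The rule for NC is: "decrease in tumour nodule size by less than 50% or increase in tumour nodule size by less than 25" per cent.
- The rule for PD is: "Progressive disease (PD): growth of the tumour nodule by more than 25" per cent.

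It does not say whether size in these categories is the volume just defined, the product of the two diameters or a single diameter. The document contains no worked volume, no third diameter and no other form of the formula. Section 3.1 limits lesions to 5 cm. Section 8 compares response by tumour location with a chi-squared test.

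**The concern.** The usual two-diameter volume treats the unmeasured third axis as equal to the shorter one, so the shorter diameter is squared. The plan's formula has the same structure with the labels reversed: the third axis is set equal to the longest. Nothing in the plan explains why the largest possible volume would be wanted, so a labelling slip is the natural reading.

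Two things are at stake. Any absolute volume reported under the printed definition would be inflated for a lesion that is not spherical. The response categories may also be affected. Volume is the only size measure for which the plan gives a calculation, and the grading follows directly from the late-effects assessment in which it appears. Someone following the text could reasonably grade on it. The extension adds 15 patients, so if response is counted per patient, one changed category among them moves a response rate by 1/15 = 6.7 percentage points.

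**Working it through.** The plan gives no volume to reproduce, so the check is direct algebra. The inputs from Section 6.1 are the formula, the definitions of a and b, and the −50% and +25% cut-offs. The 5 cm limit from Section 3.1 bounds the examples. The lesion dimensions are illustrative.

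**Single volumes.** Write S for the shorter and L for the longer diameter.

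- As printed: V = π/6 × S × L²
- Usual form: V = π/6 × L × S²
- Ratio, printed to usual: L/S

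| Lesion (cm) | Printed (cm³) | Usual (cm³) | Ratio |
|---|---|---|---|
| 5 × 5 | 65.4 | 65.4 | 1.00 |
| 5 × 4 | 52.4 | 41.9 | 1.25 |
| 5 × 3 | 39.3 | 23.6 | 1.67 |
| 4 × 2 | 16.8 | 8.4 | 2.00 |

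**How far from the truth.** Assume an ellipsoid with S and L as its shortest and longest axes and a third axis T between them. Its volume is π/6 × S × T × L. The printed form (T = L) is the upper bound and the usual form (T = S) the lower bound. For S = 3, T = 4, L = 5 the volume is π/6 × 60 = 31.4 cm³, so the printed form is 25% high and the usual form 25% low. L/S is therefore the maximum overstatement, reached only when T = S.

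**Percentage change.** The follow-up to baseline volume ratio under the printed form equals that under the usual form multiplied by (L/S after) ÷ (L/S before). If the shape is unchanged the multiplier is 1 and the category is the same. If the shape changes, the two forms diverge:

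| Change (cm) | Printed | Usual | Product of diameters |
|---|---|---|---|
| 5×3 → 3.5×3 | 36.75/75: −51%, PR | 31.5/45: −30%, NC | 10.5/15: −30%, NC |
| 4×4 → 4×2.5 | 40/64: −37.5%, NC | 25/64: −61%, PR | 10/16: −37.5%, NC |
| 4×3 → 4.5×3 | 60.75/48: +27%, PD | 40.5/36: +12.5%, NC | 13.5/12: +12.5%, NC |
| 4×3 → 4×3.5 | 56/48: +17%, NC | 49/36: +36%, PD | 14/12: +17%, NC |

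The fractions omit π/6, which cancels. Shifts occur in both directions at both cut-offs.

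**How often.** The plan gives nothing from which to estimate this. An illustrative simulation assumed baseline L/S between 1.0 and 1.6, median diameter shrinkage of 20% and an SD of log shape change of 0, 0.05, 0.10 or 0.20. Categories under the two forms differed in 0%, 3%, 6% and 11% of lesions respectively.

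**The undefined metric.** If both diameters shrink by 25%, the diameter falls 25%, the product 1 − 0.75² = 44% and the volume, under either form, 1 − 0.75³ = 58%. The same nodule is NC, NC or PR depending on what size means.

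**The case against.** The strongest reply is that the printed formula is a legitimate spheroid volume and that response is graded on relative change, so most of the inflation drops out. That is correct at constant shape. The examples above were chosen to cross a cut-off; in the simulation 89% or more of lesions kept their category across the shape variation shown.

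Second, squaring the shorter diameter is a convention, and it understates volume where the printed form overstates it. This is also right, and it is why longer/shorter is a maximum and not the exact error. It does not supply a reason for choosing the upper bound, and the plan offers none.

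Third, the link from volume to response category is not stated. Section 6.1 names modified RECIST with size and density, then WHO, and never equates size with this volume. If size is the product of diameters, all four examples are NC and the formula has no bearing on response. This stands: the effect on categories is conditional, and the undefined metric needs fixing with the formula.

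A reader might go further and infer that the inflated volumes make PR, NC and PD wrong in general, or that the main efficacy result is wrong for every lesion that changes shape. The documents support neither. The shape change must also carry the lesion across a cut-off, CR is defined by disappearance, and no primary endpoint is designated. The preliminary results in Section 2 are half complete and half partial responses, and nothing shows which formula, if any, lay behind them.

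**Conclusion.** The definition is wrong as written, most probably through swapped labels, although the document cannot prove the cause. Anyone applying it obtains volumes larger than the usual form by exactly longer/shorter: 1.25 for 5 × 4 cm and 1.67 for 5 × 3 cm. That ratio is also the ceiling on overstatement of the true volume, assuming an ellipsoid whose extreme axes are the two measured diameters.

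Misclassification of PR, NC and PD is possible in either direction, but only if three conditions hold together: size means this volume, the longer/shorter ratio changes between baseline and follow-up, and the lesion is close enough to −50% or +25% for that change to carry it across. Its frequency in this trial cannot be derived from the documents. The point should still be settled before analysis, because it governs how efficacy is graded and costs very little to correct.

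**What to change.** - In Section 6.1, redefine a as the longer and b as the shorter diameter, measured perpendicular to each other, leaving V = a × b² × π/6 unchanged. If squaring the longer diameter was intended, say so and justify it.
- In the same place, state whether size for PR, NC and PD is this volume, the product of diameters or the diameter, and make this consistent with the references to modified RECIST and WHO.
- Check the formula actually programmed in the Access database named in Section 8. If the printed definition was applied, recalculate volumes and any categories based on them, including those of the 17 patients already enrolled if it was used there. If only the text is wrong, no recalculation is needed.

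The cost is a swap of two labels, one clarifying sentence and a database check. The printed formula already needs both diameters, so recalculation should require no new imaging. The documents include no data-collection form, so it should be confirmed that both diameters, and not only the computed volume, were stored.

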## 6.2 Effects of electroporation pulses, BLM or ECT as a whole on heart function

- To study the short-term effect, we will use the ECG signal captured during surgery, which will cover the period before, during and immediately after ECT, including BLM injection and electroporation pulses.
- To study possible late and/or long-term effects, ECG signal using a standard Holter system will be recorded in 24-hour periods immediately before and after surgery. 5–10 patients will be included. ECG recordings will also be performed on 10–15 patients who will undergo abdominal surgery without ECT at the Institute of Oncology Ljubljana.

## 6.3 ECT adverse effects will be recorded in line with the criteria of the National Cancer Institute (NCI)

An adverse effect is an undesirable and unexpected sign, symptom or disease, regardless of the cause, which develops or worsens during the study and which includes pathological clinical observations and deviations in the values of laboratory-measured parameters. The latter are considered a side effect only if they require additional treatment or result in premature withdrawal of the patient from the study.

We will record any side effects that occur during the study and up to 30 days after the end of treatment. If a serious adverse reaction occurs more than 30 days after the end of treatment, the principal investigator will decide whether the complication is study-related or not.

We will record the start and end time of any adverse effect, and the cause-and-effect relationship between the adverse effect and ECT, cancer or other diseases, as well as assessing the severity of the adverse effect and describing the actions that will need to be taken.

The causal relationship between the adverse effect and the ECT will be assessed as follows:

- Not related to the study.
- Probably not related to the study.
- Possibly related to the study.
- Probably related to the study.
- Certainly related to the study.

The severity of side effects will be assessed using the following grades:

- Grade 1 – mild
- Grade 2 – moderate
- Grade 3 – a difficult complication requiring medical care
- Grade 4 – a life-threatening condition requiring immediate medical assistance
- Grade 5 – death

If a serious adverse effect is recorded during the study, the principal investigator will notify the responsible person at the National Medical Ethics Committee of the Republic of Slovenia in writing within 24 hours. A serious adverse effect is a complication that results in the following:

- death,
- a life-threatening condition requiring immediate medical assistance,
- hospitalization or extended hospitalization,
- prolonged inability of the patient to perform any task that they were able to perform before the onset of the complication,
- any event or condition which endangers the life or health of the patient and which, according to a medical assessment, could lead to any of the serious complications referred to above.

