## **7 DATA PROCESSING**

The results of the proposed clinical trial will be analyzed descriptively by describing the antitumour effect, any adverse effects and the patients' quality of life after treatment of colorectal liver metastases using ECT.

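### Read literally, Section 6.3 leaves anticipated toxicities and untreated laboratory changes out of the adverse-effect description, which can only bias it downward

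*Combined protocol and SAP*

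**What the plan says.** Section 6.3 sets the definition: "An adverse effect is an undesirable and unexpected sign, symptom or disease, regardless of the cause, which develops or worsens during the study". It continues that this is something "which includes pathological clinical observations and deviations in the values of laboratory-measured parameters", and then narrows the laboratory part: "The latter are considered a side effect only if they require additional treatment or result in premature withdrawal of the patient from the study". The recording rule is "We will record any side effects that occur during the study and up to 30 days after the end of treatment".

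The same section names the National Cancer Institute criteria, without a version, and lists five severity grades starting at Grade 1 (mild). It gives seriousness a separate definition, as a complication with one of several listed outcomes, and attaches a 24-hour written notice to the ethics committee.

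The laboratory tests are planned. Section 3.3 lists "biochemical tests: electrolytes, creatinine, transaminases" before treatment, and the schedule in Section 6.1 carries rows for blood count, coagulation tests and "Biochemical blood analysis". On reporting, Section 7 promises a descriptive analysis "describing the antitumour effect, any adverse effects and the patients' quality of life". Section 8 adds no laboratory summary.

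**The concern.** The definition joins two conditions. An event that is undesirable but anticipated fails the second one, however severe it is. A laboratory deviation faces a further condition: treatment or withdrawal. Both conditions act before anything is tabulated, so the adverse-effect description would cover a selected subset of what happened.

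Adverse effects are one of the three things that Section 7 undertakes to describe, and the treatment is applied to the liver. A reader of the final report would expect to see how often liver enzymes rose after treatment, and under the stated rule an untreated rise would not appear. With 15 patients in the extension, a few omitted patients change the picture.

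**Working it through.** The plan states no safety rate, so there is no figure to reproduce. The check is textual, followed by an illustration of scale.

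**1. Does another section restore the excluded events?** No.
- The recording sentence in Section 6.3 speaks of side effects, the term to which the laboratory condition is attached, so it inherits that condition.
- Section 7 describes adverse effects only, and Section 8 adds nothing on laboratory data.
- Section 6.2 collects ECG and Holter data separately, which covers cardiac effects and nothing else.

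**2. Is anything anticipated?** Yes. Inclusion criterion 11 in Section 3.1 requires the patient to understand possible side effects beforehand. The ECG part of Section 2 already reports a raised heart rate and mentions postoperative pain. Yet the plan has no list of expected effects and no reference for expectedness, so each recorder must decide which events fall outside the definition.

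**3. Does the section agree with itself?** Not for laboratory values. Grades 1 and 2 (mild and moderate) carry no treatment requirement, but a laboratory change must be treated or cause withdrawal to count. An untreated mild laboratory change therefore has a grade on the scale but cannot be entered.

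**4. Are the data collected after treatment?** Yes. The printed schedule is broken, so exact days are uncertain. It has seven visits, two of them before treatment. The biochemistry row has six marks, so at least 6 − 2 = 4 fall after treatment. Blood count and coagulation have three marks each, so at least 3 − 2 = 1 falls after treatment. I assume that follow-up biochemistry is the panel of Section 3.3, which includes transaminases.

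**5. Direction.** Let p be the true proportion of patients with a transaminase rise, and f the share of those patients whose rise is treated or leads to withdrawal. The reported proportion is p × f, which cannot exceed p. The two are equal only if f = 1.

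**6. Illustration.** Neither p nor f is in the documents; all values are assumptions. With n = 15 (Section 1), the true expected count is n × p, the reported expected count is n × p × f, and the chance that none is reported is (1 − p × f)^n.

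| p | True expected | Reported, f = 0.10 | Reported, f = 0.25 | Reported, f = 0.50 |
|---|---|---|---|---|
| 0.3 | 4.5 | 0.45 (63% none) | 1.12 (31%) | 2.25 (9%) |
| 0.5 | 7.5 | 0.75 (46% none) | 1.88 (13.5%) | 3.75 (1.3%) |
| 0.8 | 12.0 | 1.2 (29% none) | 3.0 (3.5%) | 6.0 (under 0.1%) |

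For example, at p = 0.5 and f = 0.10 the reported rate is 0.05, and 0.95^15 = 0.46. If the extension were pooled with the 17 patients already included (17 + 15 = 32), the same assumptions give 32 × 0.05 = 1.6 reported against 16 true, with a 19% chance of none.

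**The case against.** The strongest reply is that a filter for clinical relevance is a common and defensible choice. The extension's stated purpose is efficacy, safety is descriptive, and there is no safety hypothesis to bias. ECT is given during surgery, sometimes alongside resection, RFA or portal vein ligation, so untreated laboratory changes in this uncontrolled group would be hard to attribute to ECT. This stands as a reason not to insist on calling every laboratory change an adverse effect. It is no reason to leave scheduled results out of the report.

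The wording is also less restrictive elsewhere. Section 6.3 says that effects count whatever their cause, has a causality scale running up to certainly related, and asks for start and end times of any adverse effect. The word unexpected may be loose usage for unintended. That is plausible, but the text as it stands still directs recorders the other way.

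A reader might infer three stronger things that the documents do not support:
- *Every expected event is recorded at a rate of zero.* This is the worst-case literal reading. With no list of expected effects, no defined set of events is excluded, and staff may record more.
- *An expected serious event escapes the 24-hour notice.* Seriousness has its own definition, built on the word complication and on outcomes, with no mention of expectedness. The link to the general definition is ambiguous; it is not a clear exclusion.
- *Untreated laboratory results are lost.* They are still measured, and Section 8 puts all data in the database. They are missing from the adverse-effect description only.

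Nor can a conflict with the content of the National Cancer Institute criteria be shown here, because the documents do not reproduce them.

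**Conclusion.** The point holds in limited form. Applied as written, the two conditions in Section 6.3 make the adverse-effect description incomplete, and the bias can only be downward. The laboratory condition is the firmer part, because it is explicit and clashes with the section's own mild grade. The unexpectedness condition depends on a literal reading and on each recorder's judgement.

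The size of the under-count cannot be derived from the documents. The table shows how it behaves under assumed rates: large when few rises are treated or lead to withdrawal, nil when all are.

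The two parts also differ in how far they can be repaired. Laboratory values can be tabulated at analysis from the database. A clinical event left unrecorded because it was expected may not be recoverable, so the definition should be corrected before events are recorded under it.

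**What to change.** - Delete the unexpectedness condition from the definition in Section 6.3, and record expectedness as a separate field against a stated reference.
- Grade the scheduled blood count, coagulation and biochemistry results by the named National Cancer Institute criteria, with the version stated. Report worst grade or shift from baseline for each test, whether or not the change was treated, and add this table to Section 7 or 8. If the team wants to keep a relevance filter for what it labels a side effect, this table meets the main need.
- Use one term in place of both adverse effect and side effect.
- Reconcile the wording so that it is clear that the existing serious-event notification does not depend on the unexpectedness condition.

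The cost is a change of wording, a small addition to the case report form and one more table; no new tests or patients are needed. The safety table will be longer and look less favourable, and some of the laboratory changes in it will be due to surgery rather than ECT, which the report should say.
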